## 9.5. Study Size

CCI [REDACTED] Initial exploration of the Definitive Oncology Dataset suggest the study sample size will be between 20 and 30 patients.

The aims of this research are descriptive. Accordingly, statistical power for inferential testing comparing effectiveness outcomes across groups is not indicated. Therefore, power calculation is not applicable.

## 9.6. Data Management

Following preparation and institutional review board (IRB) approval of a study protocol, updated SQL queries will be written to identify patients within the Definitive Oncology Dataset with evidence of diagnosis of AML. Feasibility programming has already identified some likely eligible patients. However, some refinement of this programming will be undertaken to enhance identification of eligible patients. The resulting program will be used to populate a screening list used by Concerto HealthAI research staff for review of the electronic medical records.

Concerto HealthAI's Statistical Group will extract information related to demographic characteristics, infused treatments, staging, and other clinical data, as applicable. Experienced CRNs will examine the medical record of each potentially eligible patient. The disease of interest and other eligibility criteria will be verified and documented. If the patient meets all eligibility criteria, and if the accrual target has not been met, the patient will be accrued. For each eligible patient, the relevant study data will be extracted by SQL query or abstracted by CRNs onto case report forms and entered into a secure database for analysis.

Data management systems used in support of Concerto HealthAI HEOR studies are not 21 CFR part 11 validated, and are not intended for use in support of submissions to health regulatory agencies.

This project will entail use of an electronic data entry system with audit trail, but not a formal Electronic Data Capture system. Accordingly, the provisions of Section 4.4 of CT24-GSOP\_Non-Interventional Studies (Design and Develop Data Collection Tool and Data Management) are considered outside the scope of the project.

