#### 4. ABSTRACT

**Title:** Characteristics, Treatment Patterns, and Clinical Outcomes in Acute Myeloid Leukemia (AML) Patients Using Mylotarg – a US Real-World Study Using Electronic Medical Record Data

**Rationale and Background:** Historically, the number of treatments available for newly diagnosed patients with AML has been limited. However, new treatment regimens have become available recent years (including gemtuzumab ozogamicin [GO], midostaurin, glasdegib, plus low-dose cytarabine, venetoclax plus hypomethylating agents). Given the FDA label for GO, issued September 2017, it is critical to understand the recent real-world use of GO as a treatment for AML.

**Research Question and Objectives:** This research aims to assess patients with a diagnosis of AML who received Mylotarg in a real-world setting. The objectives are to:

- Describe the patient demographics and clinical characteristics;
- Describe treatment patterns and sequence;
- Describe real world effectiveness outcomes;
- Evaluate real world tumor response.

**Study Design:** This is a retrospective, observational study that will document the treatment patterns and clinical outcomes in patients diagnosed with AML who received Mylotarg. The study will use United States oncology electronic medical record data available to Concerto HealthAI, including data from CancerLinQ-affiliated practices, referred to as the Definitive Oncology Dataset.

**Population:** This study will include adult patients diagnosed with AML who, at any point on or after September 1, 2017 received Mylotarg, alone or in combination with other agents for newly diagnosed or relapsed refractory AML.

**Variables:** Patient demographics, clinical characteristics, treatment patterns, and effectiveness outcomes will be collected and analyzed.

**Data Source:** Concerto HealthAI maintains a network of oncology practices representing a geographically and demographically diverse patient population. Data from these practices have been collected centrally in the Definitive Oncology Dataset, which is the source of data to be collected in this study.

**Study Size:** The target sample size for this study is approximately 20-30 patients treated with Mylotarg.

CCI

PFIZER CONFIDENTIAL

CT24-WI-GL02-RF02 1.0 *Non-Interventional Study Protocol Template For Secondary Data Collection Study*

15-Aug-2018

Page 10 of 31

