### **9.9. Limitations of the Research Methods**

1. This study reflects treatment practice patterns only within the United States who are part of the Definitive Oncology Dataset. The majority of the data reflects treatment in community oncology settings (80%). It is possible that treatment patterns may differ in academic centers compared with community settings.
2. This study is retrospective. With the advent of newer therapies in AML, it is expected that treatment patterns will change during the next few years, and therefore, this study may not be reflective of future AML treatment patterns.
3. This study reflects a convenience sample of patients. It is possible that patients within the Definitive Oncology Dataset differ from the underlying AML population in ways that may not be measurable. For this study, all patients in the Definitive Oncology Dataset with evidence of Mylotarg utilization and an AML diagnosis will be selected, however.
4. Some measurements may not be consistently available from patient records in the Definitive Oncology Dataset.

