### 3.3. Study Size

CCI

Initial exploration of the Definitive Oncology Dataset suggests the study sample size will be between 20 and 30 patients. The aims of this research are descriptive. Accordingly, statistical power for inferential testing comparing effectiveness outcomes across groups is not indicated. Therefore, power calculation is not applicable.

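### Protocol 9.6 accrues eligible patients only until a target is met, while Protocol 9.9 says all Mylotarg-treated AML patients are selected; the two need reconciling (minor)

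*Protocol*

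**What the plan says.** Protocol 9.6 (Data Management) describes how the sample is formed. A database query is written and refined, and then "The resulting program will be used to populate a screening list used by Concerto HealthAI research staff for review of the electronic medical records". Research nurses examine the record of each potentially eligible patient and verify eligibility. The inclusion rule follows: "If the patient meets all eligibility criteria, and if the accrual target has not been met, the patient will be accrued". The next sentence provides for data collection on every eligible patient and does not mention a target.

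Protocol 9.9 (Limitations), item 3, calls the sample a convenience sample and then qualifies that: "For this study, all patients in the Definitive Oncology Dataset with evidence of Mylotarg utilization and an AML diagnosis will be selected, however".

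On the number itself, the abstract (Protocol section 4) states: "The target sample size for this study is approximately 20-30 patients treated with Mylotarg". Protocol 9.5 gives the same range as a feasibility result, saying that early exploration of the dataset would "suggest the study sample size will be between 20 and 30 patients". SAP 3.3 agrees: "Initial exploration of the Definitive Oncology Dataset suggests the study sample size will be between 20 and 30 patients". In both documents the text just before the study-size sentence is redacted.

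SAP section 5, item 3, keeps the convenience-sample limitation but omits the sentence about selecting all patients. The readable SAP contains no accrual-target rule.

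**The concern.** A rule that stops at a target and a statement that everyone is taken cannot both describe the sample unless the target is never reached. A reader of the final report could not tell whether the 20 or 30 patients are all the eligible patients in the dataset or the first ones reached on a list.

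The distinction matters because complete selection is the one thing 9.9 offers against the convenience-sample limitation. If accrual stops early, the patients left out are those lower on the list, and no review order is given. A list sorted by practice, date or identifier would leave patients out systematically. The protocol itself says in 9.9, items 1 and 2, that treatment patterns may differ between academic and community settings and are expected to change over the coming years. Practice and calendar time are therefore plausible ways for an ordered list to affect Objective 2 (treatment patterns). With so few patients expected, each omission is also a noticeable share of the data.

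**Working it through.** The plan has no sample-size calculation to reproduce. Protocol 9.5 says that a power calculation is not applicable, and 20-30 is a feasibility count. The check is therefore a comparison of the statements, followed by simple arithmetic on when the stop condition has any effect.

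**1. The statements side by side**

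| Place | Who is included | Role of 20-30 |
|---|---|---|
| Protocol 4 (abstract) | not addressed | target, approximate |
| Protocol 9.5 | not addressed | expected count |
| Protocol 9.6 | eligible patients, while the target is unmet | not stated |
| Protocol 9.9, item 3 | all patients with AML and Mylotarg use | not stated |
| SAP 3.3 | not addressed | expected count |
| SAP 5, item 3 | convenience sample, no completeness statement | not stated |

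The readable text contains no single stopping number, no review order, and no rule for eligible patients found after the target is met.

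**2. When the stop condition has an effect**

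Let M be the number of eligible patients in the dataset and C the target at which accrual stops. Then

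- number left out = max(0, M − C)
- share left out = max(0, M − C) / M

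The readable documents fix neither M nor C, so the values below are assumptions. C = 30 is the top of the stated range.

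- M = 30 or fewer, C = 30: max(0, M − 30) = 0, so nobody is left out.
- M = 35, C = 30: 35 − 30 = 5 left out; 5/35 = 14.3%.
- M = 40, C = 30: 40 − 30 = 10 left out; 10/40 = 25.0%.

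**3. With the condition removed**

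No C applies, so nobody is left out for any M, and list order no longer matters.

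**4. Could M exceed the target?**

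The documents allow it but do not say so. Protocol 9.6 reports that feasibility programming found some likely eligible patients and that "some refinement of this programming will be undertaken to enhance identification of eligible patients". That could mean finding more patients or screening out ineligible ones more accurately. Nurse verification against the eligibility criteria can only shorten the list.

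**The case against.** The strongest reply is that the stop condition is probably inert. Protocol 9.5 and SAP 3.3 give 20-30 as what the dataset is expected to yield, and the abstract's target is the same range. If target and pool coincide, no eligible patient is turned away. This stands, and it is the main reason the point is minor.

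A second reply is that selection in 9.9 may mean selection for screening. Read literally as final inclusion, that sentence would override the age criterion and the exclusions, and 9.6 does have nurses look at every potentially eligible record. This reading is possible but not conclusive. The sentence is placed as a counterweight to the convenience-sample limitation, and screening everyone while including only some would not serve that purpose.

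Third, the redacted text may hold the target number, so its absence from the readable text is not counted against the plan. A number would still leave 9.6 and 9.9 in conflict.

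Fourth, the SAP drops the completeness sentence, and Protocol 9.7 lets the SAP modify the protocol's plans. But the SAP does not say that accrual is capped or that it is not, and the protocol sentence remains.

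A reader might go further and infer that accrual will stop at 20 when 30 are eligible, losing a third of the patients, or that the response rate will be biased by some stated amount. The documents do not support either inference. No passage says that accrual stops at 20; that scenario takes the bottom of the range as the cap and the top as the pool. Nothing in the documents links list position to response, so any figure for bias would be invented. Nor can the sentence about refining the search be taken as a statement that more than 30 patients will be found.

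**Conclusion.** The inconsistency between Protocol 9.6 and 9.9 is real, and the readable SAP does not settle it. Whether it affects the data depends on one unknown: whether the eligible pool exceeds the target. If it does not, the effect is zero and only the wording is at fault. If it does, inclusion depends on an unstated list order and the completeness statement in 9.9 is wrong. The 14% and 25% figures show scale under an assumed cap of 30 and assumed pools of 35 and 40; they are not predictions. The study is descriptive and plans no statistical comparisons, so no test or error rate is at stake. Severity: minor.

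**What to change.** In Protocol 9.6, delete the second condition of the inclusion sentence, so that every patient who meets the eligibility criteria is accrued. In the abstract and in 9.5, state that 20-30 is the expected count and not a cap, and make SAP 3.3 match. Reword 9.9, item 3, to say that all patients meeting the eligibility criteria are included, since its present wording ignores the age criterion and the exclusions. In the report, give the numbers screened, eligible and included.

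If a cap has to stay, for example for budget, state the number, review the screening list in random order, and remove the completeness statement from 9.9.

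The cost is a few edited sentences and, if the pool turns out larger than expected, abstraction of a small number of extra charts. Protocol 9.6 already has nurses examining each potentially eligible record, so most of the screening work is planned. If data collection is already complete, reporting the three counts and whether the target stopped accrual would answer the question.

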### 9.6.1. Case Report Forms (CRFs)/Data Collection Tools (DCTs)/Electronic Data Record

As used in this protocol, the term DCT should be understood to refer to either a paper form or an electronic data record or both, depending on the data collection method used in this study.

A DCT is required and should be completed for the record of each curated patient. The completed original DCTs should not be made available in any form to third parties. Concerto HealthAI shall ensure that its DCTs are securely stored in encrypted electronic and/or paper form and will be password protected or secured in a locked room to prevent access by unauthorized third parties.

Concerto HealthAI has ultimate responsibility for the collection and reporting of curated data required for the study entered on the DCTs and any other data collection forms and ensuring that they meet the data curation specifications provided by Pfizer. Any corrections to entries made in the DCTs must be fully captured in an audit trail.

### 9.6.2. Record Retention

Unless expressly agreed to via a separate written agreement by Concerto HealthAI and Pfizer, Concerto HealthAI will retain all study-related documents, including copies of all DCTs, safety reporting forms, source documents utilized for curation services, and adequate documentation of relevant correspondence (eg, letters, meeting minutes, and telephone call reports), for the periods specified in this [Section 9.6.2](#) or as required by applicable law, whichever is longer, unless Pfizer authorizes, in writing, earlier destruction. Complete and accurate accounting records relating to the services Concerto HealthAI provides for this study will be maintained in accordance with generally accepted accounting principles and retained by Concerto HealthAI for at least three (3) years after completion or discontinuation of the study. Other records relating to the services Concerto HealthAI provides relating to this study will be retained for five (5) years. (In the event of regulatory filings by Pfizer, Concerto HealthAI will retain the necessary data and analysis for a period of seven (7) years or as reasonably requested by Pfizer). Concerto HealthAI will ensure that it maintains mechanisms to read any records stored in electronic form for at least the minimum retention period for those records specified in this [Section 9.6.2](#).

If Concerto HealthAI becomes unable for any reason to continue to retain study records for the required period, Pfizer should be prospectively notified. The study records must be transferred to a designee acceptable to Pfizer.

### 9.7. Data Analysis

Detailed methodology for summary and statistical analyses of data collected in this study will also be documented in a statistical analysis plan (SAP), which will be dated, filed and maintained by the sponsor. *[The SAP may modify the plans outlined in the protocol; any major modifications of primary endpoint definitions or their analyses would be reflected in a protocol amendment].*

#### 9.7.1. Descriptive Analysis

Descriptive statistics are typically generated for all study variables. The descriptive statistics include means, standard deviations, medians, and minimum and maximum values for continuous variables (eg, age at diagnosis) and frequencies and percentages for categorical variables (eg, race, performance status).

No statistical comparisons will be performed. CCI

### 9.7.2. Time to Event Analysis

Single time to event analyses will be conducted as specified under the study objectives.

CCI

Real world time to event outcomes in this study will include:

- rwEFS/rwRFS for each of the first three R/R-based lines of therapy. rwEFS will be defined as the time from the treatment initiation date (for the first line of therapy) to the date of treatment failure (TF), relapse from Complete Response (CR) or better, or death from any cause, whichever comes first. TF is defined as failure to achieve CR or better following up to 6 cycles of Mylotarg. rwRFS will be defined as the time from the treatment initiation date (for the first line of therapy) to the date of a relapse event, or death from any cause, whichever comes first.
- rwOS, from the first line of therapy through the end of record or death, whichever occurs first, and
- Duration of therapy across lines of therapy from the first line of therapy through the third R/R-based line of therapy.

The time origin for analysis of rwEFS/rwRFS is the start of therapy within each specific line of therapy, and the terminal event is the earlier of an R/R event or death. The time origin for analysis of rwOS is the start of therapy within the first line of therapy, and the terminal event is death. The time origin for analysis of duration of therapy is start of Mylotarg, and the terminal event is discontinuation of that therapy.

### 9.7.3. Methods Under Objective 1

*Objective 1: To describe the demographic and clinical characteristics as outlined in the variable list below for patients diagnosed with AML who received Mylotarg in a real-world setting.*

Descriptive analysis as detailed in [Section 9.7.1](#) will be conducted for work under this objective. Demographic characteristics that will be reported will include the distribution of sex, patient age, race/ethnicity, height, weight, BMI, insurance status, and region of residence closest to the index date. Clinical characteristics that will be reported will include the distribution of comorbidity status and comorbidity index score, ECOG score, and disease characteristics, such as stage at index date, cytogenetic testing at index date, and whether the AML diagnosis was de novo versus secondary.

Demographic and clinical characteristics will not be stratified by a primary grouping variable.

#### **9.7.4. Methods Under Objective 2**

*Objective 2: To describe the treatment patterns from the diagnosis of AML through the end of the third R/R-based line of therapy*

Analysis under this objective will include all study patients. Descriptive analysis as detailed in [Section 9.7.1](#) will be conducted for work under this objective. Treatment patterns include description of regimens within line of therapy for the first 3 R/R-based lines of systemic therapy as well as the description of sequences of regimens across 3 R/R-based lines of systemic therapy. Description of treatment regimens within line includes the frequency and percentage of each agent/regimen received, by regimen in sequence, by line, for the first 3 R/R-based lines of systemic therapy. In addition, the analysis will descriptively characterize the starting dose of Mylotarg in each of the first lines of therapy.

Duration of treatment will also be descriptively analyzed across lines of therapy, starting with the first agent or regimen in the first line of therapy for the first 3 R/R-based lines of therapy.

#### **9.7.5. Methods Under Objective 3**

*Objective 3: To describe the effectiveness outcomes of treatment of AML patients who received Mylotarg in a real-world setting.*

Analysis under this objective will include all study patients. The outcomes of interest under this objective are rwEFS/rwRFS and real world overall survival. Time to event analysis as described in [Section 9.7.2](#) will be utilized.

The Kaplan-Meier product limit estimator will be employed to evaluate rwEFS/rwRFS and rwOS. The time origin for these analyses will be the start of the treatment in the respective line of therapy for rwEFS/rwRFS for the first 3 R/R-based lines of therapy. The time origin of rwOS analysis is the start of the earliest line of Mylotarg therapy. rwEFS/RFS and rwOS analyses for lines of therapy will be limited to patients who received treatment during the line of interest.

The terminal event for analysis of rwEFS/rwRFS is the earlier of death or the first date of disease progression or R/R event following the time origin. Patients who have not died or experienced a disease progression or R/R event by the end of the medical record will be censored for analysis of rwEFS/rwRFS. The terminal event for analysis of rwOS is date of death. Note that Social Security Disability Insurance (SSDI) records have an expected lag of up to 4 months. Accordingly, patients who are not indicated to be deceased in clinical records or SSDI records will be censored for rwOS analysis as of the later of 1) the latest date known alive within the clinical record, 2) 4 months prior to the date of most recent SSDI update.

Separate Kaplan-Meier analyses will be conducted for each rwEFS/rwRFS and rwOS endpoint.

#### **9.7.6. Methods Under Objective 4**

*Objective 4: To evaluate tumor response among AML patients who received Mylotarg in a real-world setting.*

- a. First and best tumor response in the first qualifying Mylotarg-containing R/R-based line of therapy.
- b. Time to best response in the first qualifying Mylotarg-containing R/R-based line of therapy.
- c. Duration of best response in the first qualifying Mylotarg-containing R/R-based line of therapy.

Tumor response will be assessed for the first and best overall response to treatment for the first qualifying Mylotarg-containing R/R-based line of therapy during the study period. Response classifications will be made based on the treating physician's documentation of response itself, typically informed by radiological scan reports noted in the patient record. Classification is made to the following categories: complete response, partial response (PR), stable disease (SD), progressive disease (PD), and not evaluable (NE), each based on the treating physician's statements. In cases where complete response with partial hematologic recovery (CRh), complete response with incomplete hematologic recovery (CRi), and morphologic leukemia-free state (MLFS) are explicitly included in the treating physician's statements, these additional classifications will be documented. Patients for whom the record did not clearly indicate one of these classifications will be classed as NE. These patient responses will also be classified under a secondary classification as Other Favorable, or Other Unfavorable, where the record indicated the general direction of effect in order to preserve response information for each patient, even when not classifiable according to standard response categories; these responses can be assessed in descriptive analysis. The date of the best overall response for the first qualifying Mylotarg-containing R/R-based line of therapy will be collected from the index date through the end of the third R/R-based line of therapy or the end of record, whichever occurs first. Tumor responses captured are based on treating physician's assessment in the medical record. Overall response rate will be defined as a percentage of patients whose best response is either CR, CRi or MLFS, where available. Time to best response and duration of best response will be assessed using the descriptive techniques described above.

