### 9.2. Setting

#### 9.2.1. Inclusion Criteria

Patients must meet all of the following inclusion criteria to be eligible for inclusion in the study:

1. Confirmed diagnosis of AML on or after 01 December 2014 through Clinical Research Nurse (CRN) review of provider documentation of AML diagnosis in the medical record.
2. Receipt of Mylotarg at any point during first three lines of therapy following initial AML diagnosis.
3. Age  $\geq 18$  years at initial diagnosis of AML.

There are no inclusion criteria related to minimum follow-up.

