### 4.3. Analytic Methods

#### 4.3.1. Descriptive Analysis

Descriptive statistics are typically generated for all study variables. The descriptive statistics include means, standard deviations, 1st quartiles, medians, 3rd quartiles, interquartile ranges, and minimum and maximum values for continuous variables (eg, age at diagnosis) and frequencies and percentages for categorical variables (eg, race, performance status).

No statistical comparisons will be performed. CCI [REDACTED]

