rwEFS will be defined as the time from the treatment initiation date (for the first line of Mylotarg-containing therapy) to the date of treatment failure (TF), relapse from CR or better, or death from any cause, whichever comes first. TF is defined as failure to achieve CR or better following up to 3 cycles of Mylotarg. Accordingly, the time origin for rwEFS will be the start of Mylotarg in the first line of therapy in which it is used. The terminal event for analysis of rwEFS is the earlier of treatment failure, relapse from CR or better (as evidenced by provider documentation), or death. Patients who have not died or experienced an event by the date of last contact within the medical record will be censored for analysis of rwEFS.

rwRFS will be defined as the time from the treatment initiation date (during the first line of Mylotarg-containing therapy) to the date of a relapse event, or death from any cause, whichever comes first. The time origin for rwRFS will be the start of Mylotarg in the first line of therapy in which it is used. The terminal event for analysis of rwRFS will be the earlier of a relapse event (as evidenced by provider documentation), or death. Patients who have not died or experienced a relapse event by the date of last contact within the medical record will be censored for analysis of rwRFS.

The time origin of rwOS analysis is the start of the first Mylotarg use. The terminal event for analysis of rwOS is date of death. Note that Social Security Disability Insurance (SSDI) records have an expected lag of up to 4 months. Accordingly, patients who are not indicated to be deceased in clinical records or SSDI records will be censored for rwOS analysis as of the later of 1) the latest date known alive within the clinical record, 2) 4 months prior to the date of most recent SSDI update.

Separate Kaplan-Meier analyses will be conducted for each rwEFS, rwRFS and rwOS endpoint.

#### 4.3.6. Methods under Objective 4

*Objective 4: To evaluate response among AML patients who received Mylotarg in a real-world setting.*

- a. First and best response for each regimen in the first qualifying Mylotarg-containing R/R-based line of therapy.
- b. Time to best response for each regimen in the first qualifying Mylotarg-containing R/R-based line of therapy.
- c. Duration of best response for each regimen in the first qualifying Mylotarg-containing R/R-based line of therapy.

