**Table 11. Duration of Best Response from Start of First Mylotarg-Containing Line of Therapy, All Patients**

	L1 n=xx	L2 n= xx	L3 n=xx
No. of Events/No. of Patients	xxx/xxx	xxx/xxx	xxx/xxx
Median (months)	x.x	x.x	x.x
95% CI of Median	[x.x, x.x]	[x.x, x.x]	[x.x, x.x]

The time origin was the line of therapy in which Mylotarg treatment initiated.

**Figure 4. Kaplan-Meier Analysis of Duration of Best Response from Initiation of First Mylotarg-Containing Line of Therapy, First Mylotarg-Containing Line of Therapy, All Patients**

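### Text and table shells name different methods for time to and duration of best response: plain summaries can read duration too short, and the Table 11 time origin reads it too long

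*Protocol*

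**What the plan says.** **Text.** Protocol 9.7.6 and SAP 4.3.6 use the same sentence for both endpoints: "Time to best response and duration of best response will be assessed using the descriptive techniques described above". It cites no section. The sections headed Descriptive Analysis read, in Protocol 9.7.1, "The descriptive statistics include means, standard deviations, medians, and minimum and maximum values for continuous variables", and in SAP 4.3.1, "The descriptive statistics include means, standard deviations, 1 st quartiles, medians, 3 rd quartiles, interquartile ranges, and minimum and maximum values for continuous variables". The visible text of neither says how an incomplete duration is handled.

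**Where the text uses Kaplan-Meier.** Protocol 9.7.5 says "The Kaplan-Meier product limit estimator will be employed to evaluate rwEFS/rwRFS and rwOS". SAP 4.3.5 says "Separate Kaplan-Meier analyses will be conducted for each rwEFS, rwRFS and rwOS endpoint". Time to and duration of best response are not among the outcomes listed in Protocol 9.7.2 or SAP 4.3.2.

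**Shells.** SAP Figure 4 is titled "Kaplan-Meier Analysis of Duration of Best Response from Initiation of First Mylotarg-Containing Line of Therapy". Table 11 has a row for "No. of Events/No. of Patients", then a median in months with a 95% CI. Table 12 and Figure 5 treat time to best response in the same way. The footnotes to Tables 11 and 12 both put the time origin at the line in which Mylotarg was started.

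**Follow-up.** Protocol 9.2.1: "There are no inclusion criteria related to minimum follow-up". SAP 3.4.1 repeats this. Mylotarg use counts from 1 September 2017 (Protocol 4, SAP 3.4.1), and data collection was planned to end in April 2020 (Protocol 6).

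**The concern.** Duration of response is right-censored: a patient still in remission when the record stops has no end date. A plain mean or median must either treat that response as finished on the last day of the record or leave it out. Both pull the result down, and the longest remissions suffer most because they are the likeliest to be ongoing.

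The shells avoid this by using Kaplan-Meier, but start the clock at the line of therapy. What they would estimate is time from line start to loss of response, which is longer than the duration of the response.

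Objective 4c therefore has two possible answers from the same data, erring in opposite directions, and neither document says which governs. SAP 4.1 counts response among the primary endpoints, though it does not name duration. With 20 to 30 patients, a few ongoing remissions can move a median.

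**Working it through.** The plan gives no duration of response and no censoring share, so there is no figure of its own to reproduce. The check has three parts.

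**1. Inputs**
- Longest follow-up: September 2017 to April 2020, F = about 31 months. The end date is a planned milestone.
- Responders: Protocol 7 cites a background remission rate of 60%-70%. With 20 to 30 patients this gives 0.6 × 20 = 12 to 0.7 × 30 = 21. It is used only to set the scale.
- Assumed: durations T exponential with true median m of 3 to 24 months; follow-up after response C uniform on 0 to F.

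**2. If the text is followed**

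When ongoing responses are counted as complete, the plain median is the t that solves

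exp(−ln2 · t/m) · (1 − t/F) = 0.5.

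For m = 12 and F = 31, t = 7.3: exp(−0.693 × 7.3/12) = 0.656, 1 − 7.3/31 = 0.765, and the product is 0.50. The shortfall is 1 − 7.3/12 = 39%.

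The censored share is (1 − exp(−λF))/(λF) with λ = ln2/m. For m = 12, λF = 1.79 and the share is 0.833/1.79 = 47%.

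The column for dropped responses comes from simulation.

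| True median (months) | Censored | Plain median, ongoing counted as complete | Plain median, ongoing dropped |
|---|---|---|---|
| 3 | 14% | 2.6 (−13%) | 2.6 (−15%) |
| 6 | 27% | 4.6 (−23%) | 4.3 (−29%) |
| 12 | 47% | 7.3 (−39%) | 6.0 (−50%) |
| 18 | 58% | 9.0 (−50%) | 6.9 (−62%) |
| 24 | 66% | 10.2 (−58%) | 7.4 (−69%) |

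With F = 28 the third column runs from −14% to −60%.

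The result depends on how early censoring falls as well as on how much there is. If every responder has at least 12 months of follow-up after response (C uniform on 12 to 31), true medians of 3, 6 and 12 months read 3.00, 6.01 and 11.96 when ongoing responses are counted as complete, even with 30% censored in the last case.

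Kaplan-Meier on the same model (C uniform on 0 to 31; 12, 16 or 21 responders; 4,000 runs each):

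| True median (months) | Typical Kaplan-Meier median | Median not reached |
|---|---|---|
| 6 | 5.9-6.0 | about 0% |
| 12 | 12.0-12.1 | 4%-10% |
| 18 | 18.1-18.2 | 21%-29% |

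**3. If the Table 11 shell is followed**

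For each responder, time from line start to loss of response = time to best response + duration of response. If every responder took r months to respond, event and censoring times would all move by r, and the Kaplan-Meier median would be m + r. The error is always upward. Its size is the time to response, which the documents do not give.

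**Event and censoring rule.** Neither document's visible text states one for duration of response. The derived-variable entries (Protocol 9.3.4, SAP 3.5.2) give only a window that closes at the end of the third line or of the record. Table 11 counts events without defining them.

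**The case against.** The strongest reply is that the SAP already plans the right estimator. Table 11 and Figure 4 are the only outputs planned for duration of response, and no shell asks for a plain mean or median of it. Where the SAP wants a mean-and-quartile layout it supplies one, as in Table 5 for treatment duration. It is the later and more detailed document, and Protocol 9.7 allows it to modify the protocol's plans. The shared sentence cites no section and follows the Kaplan-Meier section, so its reference to earlier techniques could be read to include Kaplan-Meier. Some text in the descriptive and time-to-event sections is also blacked out.

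Much of this stands. The short bias reaches the report only if the text is followed instead of the shell, and redacted text could say more about estimation.

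It does not remove the point. The SAP's methods text repeats the protocol sentence, so giving the SAP precedence leaves it in conflict with its own shells. Both documents keep descriptive analysis (Objectives 1 and 2) apart from time-to-event analysis (Objective 3), so plain statistics remain the more natural reading. Table 5 also shows a duration summarised by mean and median with study end as a possible end point. And following the shell brings in its own error through the time origin.

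A reader might infer that duration of response will be reported as far too short. The documents do not support that: they give neither an expected duration nor a censoring share, the shortfall can be negligible, and the planned output is a Kaplan-Meier analysis.

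**Conclusion.** The point holds as a conflict over method with two conditional biases.

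- **Certain from the documents:** the methods text points to plain summaries for both endpoints, while Tables 11 and 12 and Figures 4 and 5 are Kaplan-Meier. The visible text gives no event or censoring rule for duration, and Table 11 starts the clock before the response begins.
- **If the text is followed:** the plain median is too short or unbiased, never too long. With ongoing responses counted as complete, the shortfall runs from about 0% to about 60%; dropping them is worse in the scenarios tabulated. The 12-to-7.3 example rests on exponential durations and uniform 0-31 month censoring, which are assumptions.
- **If the shell is followed:** censoring is handled, but duration is too long by the time to response, an amount the documents do not give.

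This should be settled before analysis because it leaves the estimator for Objective 4c open. It does not show that a biased figure will be reported, and it does not affect the methods for rwEFS, rwRFS or rwOS.

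**What to change.** 1. In Protocol 9.7.6 and SAP 4.3.6, state that duration of best response is estimated by Kaplan-Meier (median, 95% CI) among responders, from the date of best response to relapse/progression or death, censored at last contact if still in response. Add it to the outcome lists in Protocol 9.7.2 and SAP 4.3.2.
2. Change the time origin and titles of Table 11 and Figure 4 to match: date of best response, responders only.
3. Make the text and Table 12/Figure 5 name one method for time to best response, and state its population. Among responders every such time is observed; over all treated patients, those without a response need a censoring rule.
4. Do not report a plain mean or median of observed response durations.

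The cost is a few sentences and relabelled shells. The dates of best response, R/R events, progression and death are already listed for collection, and last contact is already used to censor rwEFS and rwRFS. The downside is that the Kaplan-Meier median may not be reached with few responders: in 4%-10% of runs at a true median of 12 months and 21%-29% at 18 months, under the assumptions above. That should then be reported as such.
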